8.7.5. Cost Data

Because health care costs are often skewed, estimated cost measures will be modeled using a gamma regression model. Coefficients from a generalized linear model (GLM) are estimated cost ratios. Cost ratios, 95 percent confidence intervals, and p-values will be presented for each covariate included in the final model. For ease of interpretation and comparison with the bivariate results, the average cost will be predicted for each cohort and may also be predicted for pre-determined levels of other patient characteristics (eg, combination vs. monotherapy, gender).

If a significant number of patients have zero values for costs, estimated cost measures will be compared using a two-part model (ie, one equation estimating the probability of any cost and a GLM with a gamma distribution and log link estimating the level of cost). This method avoids potential difficulties introduced by transformation and retransformation of the dependent variable.

If there is an excessive number of zero-dollar cost patients, then only logistic regression prediciting the probability of nonzero costs will be run.

Odds ratios, 95 percent confidence intervals, and p-values will be presented for each covariate included in the logistic model estimating the probability of non-zero costs. Cost ratios, 95 percent confidence intervals, and p-values will be presented for each covariate included in the GLM model estimating the level on costs. Combined results will displayed.

8.7.6. Dichotomous Data

The probability of being effectively treated, persistent, and anytime switching to advanced therapy at one year will be modeled using logistic regression. Logistic regression models fit a maximum-likelihood logit model. For ease of interpretation, the results of logistic regression will be presented as odds ratios, 95 percent confidence intervals, and p-values for each covariate included in the final model.

8.8. Quality Control

This is a retrospective study, so issues of quality control at study sites, eg, data queries, do not apply. Analyses are programmed according the specifications in the protocol, and if applicable, the statistical analysis plan and documented in a programming plan. Final deliverables are reviewed and verified by a second, independent programmer who may also perform double programming. All quality checks are documented in the programming plan.

8.9. Limitations of the Research Methods

Limitations that are general to claims database analyses and specific to this study should be noted. First, diagnosis of autoimmune conditions will be identified using ICD-9/10-CM diagnosis codes, which are subject to potential miscoding. Second, clinical and laboratory data are not available, thus we are relying on adjudicated claims data for characterizing medical history, treatment exposure and outcomes. Along these lines, we may be missing information on services or resources for which claims were not submitted such as medication samples. We will use 2-year pre-index continuous enrollment to increase the likelihood of capturing patient baseline characteristics including prior advanced therapy experience. However, this may not be sufficient and may bias the sample to patients who stay in health plans and may be healthier.

Further, we require 1-year of post-index enrollment across groups to ensure similar follow up, but this may not be representative of health plan enrollees and may bias toward longer treatment duration or higher healthcare resource use and costs. This study will include an examination of medication effectiveness at 1 year among all biologic users. Effectiveness will be measured using a validated algorithm; however, the algorithm was not validated for all medications being included. Specifically, tofacitinib was approved for treatment of RA after the algorithm was developed. Although this study will also evaluate outcomes using multivariable analysis to control for observable

differences between groups, there may be unobservable differences as common with observational research designs.

8.10. Other Aspects

Not Applicable.

9. PROTECTION OF HUMAN SUBJECTS

All parties will ensure protection of patient personal data and will not include patient names on any sponsor forms, reports, publications, or in any other disclosures, except where required by laws. In case of data transfer, Pfizer will maintain high standards of confidentiality and protection of patient personal data.

As this is a retrospective non-interventional study using fully anonymized secondary data, no additional informed consent is required.

9.1. Patient Information

This study involves data that exist in anonymized structured format and contain no patient personal information.

9.2. Patient Consent

As this study involves anonymized structured data, which according to applicable legal requirements do not contain data subject to privacy laws, obtaining informed consent from patients by Pfizer is not required.

9.3. Institutional Review Board (IRB)/Independent Ethics Committee (IEC)

IRB is not required for this study as it uses commercially available de-identified secondary data sources and is considered exempt from the requirements for "human subjects research" in the US.

9.4. Ethical Conduct of the Study

The study will be conducted in accordance with legal and regulatory requirements, as well as with scientific purpose, value and rigor and follow generally accepted research practices described in Good Practices for Outcomes Research issued by the International Society for Pharmacoeconomics and Outcomes Research (ISPOR).

10. MANAGEMENT AND REPORTING OF ADVERSE EVENTS/ADVERSE REACTIONS

This study involves data that exist as structured data by the time of study start. In these data sources, individual patient data are not retrieved or validated, and it is not possible to link (ie, identify a potential association between) a particular product and medical event for any individual. Thus, the minimum criteria for reporting an adverse event (AE) (ie, identifiable patient, identifiable reporter, a suspect product, and event) cannot be met.

11. PLANS FOR DISSEMINATING AND COMMUNICATING STUDY RESULTS

For all publications relating to the Study, Pfizer will comply with recognized ethical standards concerning publications and authorship, including Section II - "Ethical Considerations in the Conduct and Reporting of Research" of the Uniform Requirements for Manuscripts Submitted to Biomedical Journals,

http://www.icmje.org/index.html#authorship, established by the International Committee of Medical Journal Editors.

In the event of any prohibition or restriction imposed (eg, clinical hold) by an applicable competent authority in any area of the world, or if the investigator is aware of any new information which might influence the evaluation of the benefits and risks of a Pfizer product, Pfizer should be informed immediately.

13. LIST OF TABLES

SEE ATTACHED EXCEL WORKBOOK FOR DRAFT TABLES

- TABLE 1. DEMOGRAPHICS
- TABLE 2.RA CHARACTERISTICS
- TABLE 3. COMORBIDITIES TABLE
- TABLE 4. TREATMENT PATTERNS
- TABLE 5. HEALTHCARE RESOURCE USE
- TABLE 6.COSTS

14. LIST OF FIGURES

15. ANNEX 1. LIST OF STAND ALONE DOCUMENTS None.

16. APPENDICES

Appendix 1. ADVANCED THERAPIES

Generic Name^	Brand Name	Route of Admin.	GPI codes^	НСРСЅ
TNFi				
Adalimumab	Humira	SC	66270015	J0135
Etanercept	Enbrel	SC	66290030	J1438
Golimumab	Simponi, Aria	SC/ IV	66270040	J1602
Certolizumab pegol	Cimzia	SC	52505020	C9249, J0717, J0718
Infliximab	Remicade, Renflexis, Inflectra	IV	52505040	J1745, Q5102
Alternative MOA		•		
Tofacitinib	Xeljanz	РО	66603065	None
Baricitinib	Olumiant	РО	66603010	None
Abatacept	Orencia	IV/SC	66400010	C9230 J0129
Anakinra	Kineret	SC	66260010	None
Tocilizumab	Actemra	IV/SC	66500070	C9264 J3262
Rituximab	Rituxan	IV	21353060	J9310
Sarilumab	Kevzara	SC	66500060	None
Unspecified				J3590, J3490

^GPI codes from MediSpan;

https://www.azahcccs.gov/PlansProviders/Downloads/PharmacyUpdates/AHCCCSPreferredDrugs_04_01_201 8.pdf;

https://www.bluecrossmn.com/healthy/public/portalcomponents/PublicContentServlet?contentId=P11GA_1630 6146.

Appendix 2. NON-BIOLOGIC (TRADITIONAL) DMARDS

Generic Names^	GPI Codes^	J-codes
Hydroxychloroquine	13000020	n/a
Methotrexate	21300050 66250050	J8610, J9250, J9260
Leflunomide	66280050	n/a
Sulfasalazine	52500060	n/a
Other Medications:		
Chloroquine	13000010	J0390
Combos	1399000220	n/a
Cyclosporine	99402020	J7502, J7515, J7516, C9438, J7503, K0121, K0122, K0418
Thalidomide	99392070	n/a
Azathioprine	99406010	J7500, J7501, C9436, K0119,
Cyclophosphamide	21101020	J8530, J9070, J9080, J9090, J9091, J9092, J9093, J9094, J9095, J9096, J9097, C9420, C9421
Auranofin	66200010	n/a
Aurothioglucose	66200020	J2910
Gold Sodium Thiomalate	66200030	J1600
Penicillamine	99200030	n/a
Tacrolimus	99404080	J7507, J7525, C9006, J7508
Minocycline/Tetracyclin	04000040	J2265

^ GPI codes from MediSpan.

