NB-DMARD use	Outcome	All	 For patients who initiate combination therapy, will look for select NBDMARD (MTX, SSZ, LEF, HCQ) discontinuation or switch from start of NB-DMARD through end of 12-month post-index period. Definitions of treatment patterns are similar to 5 persistent groups above for index advanced therapy medications and using a 60 day gap. A 28-day supply will be assumed for MTX administrations. For those who initiated advanced monotherapy, addition of one for four main or other NBDMARDs will be evaluated.

Variable	Role	Data source(s)	Operational definition
Medication Effectiveness Proxy Algorithm (Curtis et al) ¹⁴	Outcome	All	Medication effectiveness at one year after the index date will be determined using the following six criteria. For each of the 6 criteria, a 0/1 flag will be created. Patients who are effectively treated for each of the 6 criteria will be considered effectively treated. Patients who fail any of the 6 criteria are therefore not effectively treated.
			1.High adherence to index agent: For all medications, a proportion of days covered (PDC) will be calculated based on total days supply over the 1 year follow-up. The PDC will be calculated by using the date of service and the day supply for each fill of the index medication. Patients with early refills will be allowed to stockpile medications up to a maximum of 14 days total for later use. Patients with PDC ≥ 0.8 will be considered highly adherent and effectively treated. The original Curtis algorithm referenced an MPR;however, more recent studies are using PDCs or similarly described measure. ¹⁵

Variable	Role	Data source(s)	Operational definition
		I	2.No increase in dose (see below)
			for index medication compared to the
			starting dose. Dose escalation will be
			identified per the criteria listed
			below.
			ADA: At least 1 claim in the follow-up period with an average weekly dose of at least 40 mg/week. ETN: At least 1 claim in the follow-up period with an average weekly dose of at least 100 mg/week.
			TOFA: At least 1 claim in the
			follow-up period with an average
			weekly dose of at least 20 mg/day
			for IR and 22 mg/day for XR.
			for the and 22 mg/day for XR.
			3.No switching from the index medication to a different advanced therapy. A switch will be defined as use of a different bDMARD or JAKi any time during the follow-up period noting the availability of newer advanced therapies after original 2011 Curtis algorithm publication.

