			4.No adding of a new non-biologic DMARD to the index therapy.
			Measure has been modified to
			distinguish outcomes for advanced
			monotherapy vs. NB-DMARD
			comobination regiments, noting
			patients may not have NB-DMARD in
			6-mos pre-indes but start a
			combination regimen. For those
			starting a monotherapy index
			medication regimen, the initiation of a
			select NB-DMARD will be identified
			in the follow up period as addition of
			NB-DMARD. For those starting a
			combination index medication
			regimen, presence of a different NB-
			DMARD in follow-up will be flagged
			as failing the algorithm.

Variable	Role	Data source(s)	Operational definition
			5. Oral glucocorticoids. Only National Drug Code (NDC) codes for oral glucocorticoids will be included.
			5a. For patients with no claims for oral glucocorticoid prescriptions in the six months prior to the index date: cannot receive more than 30 days of oral glucocorticoids between (index date + 89) to (index date + 359). 30 days of oral glucocorticoids will be determined by summing up the day supply of all glucocorticoids claims with a fill date between (index date + 89) to (index date + 359).
			5b. For patients with claims for oral glucocorticoids during the six months prior to the index date: No increase in oral glucocorticoid dose ≥20% during months 6- 12 after index compared to the 6 months before the index date. Increase in oral glucocorticoids will be determined from the prednisone equivalent dose for all glucocorticoid claims filled during the respective time periods.
			6. At most one parenteral or intra- articular glucocorticoid joint injection on unique days after the patient had been on biologic treatment for more than three months between (index date + 89) to (index date + 359). CPT codes 20600, 20605, 20610.
Change in Resource Use RA-related healthcare	and Costs (Tables 5 an Outcome	all	The number of patients with and number of encounters
resource use		- 141	(including zeros) for each RA- related medical and pharmacy resource use will be evaluated in the 12-month pre- and post-index periods. See Section 8.3.1 for details on calculating cost and healthcare utilization.
All-cause healthcare resource use	Outcome	All	The number of patients with and number of claims (including zeros) for each all-cause medical and pharmacy resource use will be evaluated in the 12-month pre- and post-index periods. See Section 8.3.1 for details on calculating cost and healthcare utilization.

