Anxiety	300.02, 293.84, 309.21, 300.0, 300.00,	F410, F422,F423, F428, F429, F4310, F4312, F4010, F4001, F4002, F409, F4001, F4002, F4010, F408, F40218, F40240, F40241, F409, F411, F064, F930, F419, F410, F411, F418, F99, F489, F449, F444, F446, F440, F441, F4481, F449, F4489, F6811, F688,R42, R000, R002, R064, R0602, R063, R0600, R0609, R0683, R0689
Sleep disorders		F519, F5102, F5109, F5101, F5103, F5109, F5119, F5111, F5112, F5119, F518, F513, F518, G479, G4730, G4700, G4730, G4710, G4720, G478, G4730, F518, G478, R0681, Z72820
Interstitial lung disease	516.9	J84.9

	GPI Codes ^	HCPCS	Prednisone Eq Dose
SYSTEMIC GLUCOCORTIC	OIDS		
High Potency			
betamethasone	22100010	J7624	0.60
dexamethasone	22100020	J1094, J1095, J1100, J8540, Q0137, Q0138, S0173	0.75
Medium Potency			
Fludrocortisone	2220003010		n/a
methylprednisolone	22100030	J1020, J1030, J1040, J2920, J2930, J7509	4
prednisolone	22100045	J1680, J2640, J2650, J7510	5
prednisone	22100040	J1690, J7506, K0125	5
Triamcinolone	22100050	J3300, J3301, J3302, J3303	4
Low Potency			
Cortisone	22100015	J0810	25
Hydrocortisone	22100025		20
NSAIDs/Salicylates	6610, 66998, 6410	J1885, J1130, J0131, C9283, J1741, C9279	N/A
Opioids			N/A
Strong (morphine, methadone, fentanyl, hydromorphone, oxymorphone, oxycodone, hydrocodone, buprenorphine, butrophanol, nalbuphine, levorphanol)	65100055,655100050, 65100025,65100035,6 5100080,6500075,651 00030,65200010,6520 0020,65200030,65100 040	J2275 ,Q9974 S0093 , J1230 ,S0109 J1170 S0092 J2410	N/A

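### Two small code-list defects in secondary outcomes: fludrocortisone has no prednisone equivalent for criterion 5, and criterion 4 scores the same minocycline/tetracycline claim differently by regimen

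*Combined protocol and SAP*

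**What the plan says.** **NB-DMARDs.** Appendix 2 separates four main drugs from a group of other medications. The second group includes "Minocycline/Tetracyclin", with one GPI code and administration code J2265. No minimum supply or diagnosis condition is attached.

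Criterion 4 of the effectiveness proxy (Section 8.3) is headed "No adding of a new non-biologic DMARD to the index therapy" and has two branches:
- For monotherapy starters, initiation of a "select NB-DMARD will be identified" in follow-up as an addition.
- For starters of a combination index "regimen, presence of a different NB"-DMARD in follow-up fails the algorithm. This branch is not limited to the four main drugs.

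The NB-DMARD use row of the same table gives a meaning for *select*: for combination starters the study "will look for select NBDMARD (MTX, SSZ, LEF, HCQ) discontinuation or switch". For monotherapy starters that row is wider: "addition of one for four main or other NBDMARDs will be evaluated".

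**Glucocorticoids.** Appendix 5 places "Fludrocortisone" among the medium-potency systemic glucocorticoids, with GPI 2220003010 and prednisone equivalent n/a. Criterion 5a applies to patients without an oral glucocorticoid claim in the prior six months. It fails them above 30 days between index+89 and index+359, counted by "summing up the day supply of all glucocorticoids claims". Criterion 5b applies to patients with such a claim and compares prednisone-equivalent dose before and after index, failing a rise of 20% or more.

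Failing any one of the six criteria makes a patient not effectively treated. Section 8.3.1 also sends the Appendix 2 and Appendix 5 drugs into RA-related use and cost, pre- and post-index.

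**The concern.** The two branches of criterion 4 appear to work from different drug lists, so an identical claim can fail one patient and not another solely because of starting regimen. The combination branch is also wider than the definition of the group it applies to, since Section 8.3 assigns combination status on the four main drugs only. Criteria 5a and 6 tolerate limited use (30 days, one injection), whereas the combination branch of criterion 4 tolerates none.

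For fludrocortisone, 5b requires a conversion that Appendix 5 does not supply, and no rule says what to do with an n/a entry. Section 8.7.3 rules out imputation, so some patients could have no defined flag for criterion 5.

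At stake are the effectiveness proxy (Section 7.2, modelled by logistic regression in Section 8.7.6), the NB-DMARD addition outcome, and RA-related use and cost. As written, a programmer would have to choose a rule.

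**Working it through.** The plan states no expected effectiveness, event rate or sample size, so there is no figure of its own to reproduce. The check traces each drug through the rules and then sizes the effect on assumed inputs.

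**1. Fludrocortisone under 5a.** The window from index+89 to index+359 is 359 − 89 + 1 = 271 days.
- One 30-day fill: 30 days, not above 30, so no failure.
- Two 30-day fills: 60 days, above 30, so failure.

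The missing prednisone equivalent plays no part here, because 5a counts days.

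**2. Fludrocortisone under 5b.** Change = (post − pre) / pre, in prednisone equivalents.
- If fludrocortisone is the only pre-index claim, the patient moves from 5a to 5b. Then pre is undefined, or 0 if n/a is treated as zero, and the ratio cannot be computed.
- If another glucocorticoid supplies the baseline and n/a is treated as zero, fludrocortisone cannot itself create a 20% rise.

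So the 5b defect is an undefined calculation and a misrouting between 5a and 5b. It is not an automatic failure.

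**3. One minocycline/tetracycline claim in follow-up.**

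| Outcome | Combination starter | Monotherapy starter |
|---|---|---|
| Criterion 4 | Fails | Does not fail, if *select* means the four main drugs |
| NB-DMARD use row | Row tracks the four main drugs only | Counted as an addition |
| RA-related use and cost | Counted | Counted |

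**4. Size for the effectiveness proxy.** Assumed, not in the documents: true effective share p = 20-40%; combination share c = 40-60%; share m = 1-5% of otherwise effective patients with such a claim.

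If only combination starters are exposed, drop = p × c × m:
- lowest: 0.20 × 0.40 × 0.01 = 0.08 points
- highest: 0.40 × 0.60 × 0.05 = 1.2 points
- highest with m held to 3%: 0.40 × 0.60 × 0.03 = 0.72 points

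If *select* were read as all of Appendix 2, drop = p × m:
- lowest: 0.20 × 0.01 = 0.2 points
- highest: 0.40 × 0.05 = 2.0 points

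**5. Size between cohorts.** Assume two cohorts differ by 10 points in combination share, with p = 30% and m = 1-3% in both. The distortion is 0.10 × 0.30 × 0.01 = 0.03 points to 0.10 × 0.30 × 0.03 = 0.09 points. If m itself differs between cohorts the figure changes, and the documents say nothing on that.

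**6. Size for the NB-DMARD addition outcome.** Assume a true rate t = 10% and a share a = 1-3% with a claim that is not an RA addition. Measured rate = t + (1 − t) × a:
- a = 1%: 0.10 + 0.90 × 0.01 = 10.9%
- a = 3%: 0.10 + 0.90 × 0.03 = 12.7%

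This is a shift in level. It is not a shift between cohorts.

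**The case against.** A reader might infer that claims unrelated to RA are generally scored as treatment failure. The case against that reading is strong, and most of it stands.

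- Criterion 4 reaches combination starters only, on the meaning of *select* given in the same table. That meaning is borrowed from the neighbouring row, and the heading of criterion 4 is broader, so some ambiguity remains.
- A fludrocortisone fill is not a failure in itself. Under 5a it takes more than 30 days, and the n/a entry causes no failure under either sub-rule.
- The documents do not show that minocycline/tetracycline claims are unrelated to RA. Appendix 2 classes the drug as a DMARD, and the mix of indications is not given. Nor do the documents say what the Combos row of Appendix 2 covers.
- Criterion 5 does not cite Appendix 5. It refers only to oral glucocorticoids identified by NDC, and n/a could have been meant as an exclusion. However, the prednisone-equivalent column has no other stated use, and Section 8.3.1 does cite Appendix 5 for RA-related use and cost.
- The effect is small.

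What remains is that the two branches of criterion 4 use different lists with no stated reason, the other Appendix 2 drugs carry no minimum supply, and no rule covers an n/a equivalent.

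**Conclusion.** This is a minor specification defect, worth correcting before programming. Primary persistence is unaffected: it depends on index-drug fills and on switches to Appendix 1 therapies, and neither list enters it.

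For the effectiveness proxy, the minocycline/tetracycline rule costs about 0.1-1.2 percentage points under the assumed rates, and stays below 1 point if no more than 3% of otherwise effective patients have such a claim. The upper figure of 2.0 points needs both a 5% claim rate and the wider reading of *select*. Differences between cohorts would be a few hundredths of a point if claim rates are similar; their direction cannot be derived from the documents. No rate for fludrocortisone is given, so its effect is not sized, and it arises in criterion 5 only if Appendix 5 is the list used there.

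The documents do not support going further, to a claim that effectiveness is materially biased for or against any cohort.

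**What to change.** 1. **Fludrocortisone.** Remove it from the glucocorticoid list used for criteria 5a and 5b, and state that criterion 5 uses the Appendix 5 list so amended. Remove it from RA-related corticosteroid use and cost as well, in both the pre- and post-index periods.
2. **Criterion 4.** Name one drug list and use it in both branches. Extending all of Appendix 2 to both branches without a supply condition would enlarge the effect, as the 0.2-2.0 point range shows.
3. **Minimum supply.** If the other Appendix 2 drugs stay in criterion 4 or in the NB-DMARD addition outcome, prespecify a minimum supply for minocycline/tetracycline, with a stated rule for J2265 administrations, which have no assigned days' supply. The plan's 60-day figure defines a treatment gap and does not by itself justify a supply threshold.
4. **Use and cost.** Apply any such condition identically before and after index. A condition on follow-up alone would distort the post-minus-pre change.

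The cost is one code removed, a sentence or two in Section 8.3, and a supply condition in programming if the wider list is kept. The downside is that a few genuine RA uses that are short, or start late in follow-up, would be missed.
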